**Protocol Version: 4**

**Funded by: National Institute on Minority Health and Health Disparities**

## **1.0 Project Overview**

In the United States, the postpartum period is a critical time for both maternal and child health, the mortality rate is the highest among other developed, high income countries and more than half of all maternal deaths occur postpartum, from one day to one year after birth. This poor outcome is linked to the racial and ethnic disparities that disproportionately affect black women who are 3-4 times more likely to experience maternal mortality than white women. Recently, the American College of Obstetricians and Gynecologists recognized the deficiencies in postpartum care and coined the term the ‘fourth trimester’ to mark the time following the birth of the infant through the first 3-months postpartum, and updated its recommendations to address these challenges. With impacts to health outcomes and healthcare costs, there is a need to holistically bridge the gap for low-income and/or ethnically diverse groups of women to address the physical, cultural, and knowledge barriers to accessing quality postpartum care. To improve the rate at which underserved women are disproportionately affected by maternal mortality and morbidity, we need to engage women leading into and specifically during the postpartum period to identify areas of need, and to provide tools which reduce barriers for women to get appropriate postpartum care. Technology offers innovative solutions to challenges around equal information access. Pregnant women often turn to the internet to find out more information about their health and their developing babies health. Yet, studies find that mothers are not finding sufficient resources to match their postpartum needs. To address this gap in care, we will develop a mobile tool designed to increase accessibility to information and practical approaches for addressing the complex needs of women in this ‘fourth trimester’. This tool will specifically focus on underserved women who are at greatest risk of adverse postpartum outcomes. We propose to complete three major tasks:

**AIM 1:** Gather input from key stakeholders to inform the design, key content, and interactive technological components of the mobile tool. To achieve this aim we will conduct formative qualitative research with pregnant women and women who have gone through the postpartum experience.

[figure not shown]
**AIM 2:** Develop a prototype to demonstrate the goals of the complete tool including sample content and interactivity, a detailed outline of content, and interactive features including real world examples and peer support. In collaboration with our clinical experts, we will draw on the knowledge gained in formative research in combination with relevant evidence-based practices to develop the prototype.

**AIM 3:** Demonstrate the acceptability, usability, feasibility and dissemination potential of the tool with input from key stakeholders and end-users in preparation for the Phase II effectiveness study. We will use quantitative and qualitative methods to assess the feasibility of the content, approach, and effectiveness of the program and identify the key measures for the Phase II study.

## **2.0 Research Design and Methods**

The image below outlines each of the major activities occurring during each step, including those involving human subjects research. All study staff will be trained and certified in the protection of human subjects, and will be required to complete human research subjects training through either the Collaborative Institutional Training Initiative (CITI) Training Program or the Association of Clinical Research Professionals (ACRP) Human Subjects Protection Training. All data collection will be conducted by trained HealthCore and Orange Square research study staff and, in the case of limited interviews/focus groups, by an Orange Square subcontractor with specific expertise in this population. This subcontractor is serving as part of the Orange Square study team in a limited role. All electronic data collection will be conducted under Orange Square’s study-specific Qualtrics license. Only HealthCore and Orange Square research staff will have access to this Qualtrics account. [name], HealthCore study PI and qualified qualitative researcher, will conduct study specific training for all study staff involved in the screening, recruitment, and conducting of focus groups and interviews. Training will include: a review of the study protocol, recruitment processes, screening procedures, participant communications, informed consent, and the appropriate methodology for conducting focus

groups and other study data collection activities. [name] will have direct oversight over all data collection activities.

### 3.0 Current Status

Analysis, manuscript preparation and program development are currently underway. Additional protocol information is reserved to protect proprietary data and IP.

1 INTRODUCTION

This document outlines the detailed statistical methods to be implemented during the analysis of the Phase I Joyuus study data, with the goal of providing the appropriate information to demonstrate the acceptability, usability, feasibility and commercialization potential of the Joyuus mobile web-based tool and informing the design of the Phase II effectiveness study.

2 STUDY OBJECTIVE

We are developing a prototype of a mobile tool to help moms in the postpartum period, or the 3 month period after having a baby. This program will provide tools, resources, and information to help you take care of yourself during this period.

We are conducting a research study to test a prototype version of the tool to see if users like it and think the information is trusted. We also want to know how it can be improved. We will also be learning from you if the tool provides helpful information about self-care, including managing stress, depression, and anxiety.

3 STUDY DESIGN

In order to evaluate the objectives outlined for Phase I of this study, we will conduct a mixed methods Pilot to understand whether:

- a) The content is delivered at the appropriate level and depth for the audience;
- b) The prototype and planned broader development of the tool provides engaging and helpful approaches to self-care, including managing stress/distress, depression and anxiety related to the postpartum period;
- c) We met the developmental aims of the prototype on which to build a larger program (is it clinically accurate, is it user friendly, will they use it; what should be modified).

The Pilot will include pre- and post-tests and will solicit user feedback from 80-90 birthing people. Each participant will be provided access to the product for one month. During this time, they will be asked to complete a pre-test survey at initiation and answer 2 online surveys about their experiences using the tool. They will also complete a post-test after one month of having access to the tool. This will not be a fully functioning site, but a prototype to test the feasibility of the concept that will be fully developed with future funding.

We will also conduct 75-90 minute individual or group discussions, by telephone or video conference, with a subset of 24-36 participants who have completed the pre-test, to further understand participants' perspectives on the consumer experience, the content and presentation of information, functionality, design and interactivity.

In order to be eligible to participate in this research study, potential participants must be:

- Inclusion Criteria
 - Age 18+;

- Racial/ethnic minority (at least 75% of participants must be non-white, with at least 50% identifying as Black/African American);
- Be a new or expectant birthing person – participants must be at least 28 weeks/6 months pregnant (3rd trimester), and up to 1 year post-birth (to allow for those who participated in the Needs Assessment to be eligible for continued participation) (*no more than 50% of participants will be currently pregnant, at least 50% will be postpartum*).
- Have a smartphone with internet access and are willing to use this device to participate in all study activities.
- Able to adhere to the terms of the study (available time commitment, have internet access; willing to comply with the specified focus groups and survey); and
- Able to read, write and speak English (all research and product development activities will be conducted in English due to budgetary constraints).
- Exclusion Criteria
 - Unable to comply with the Inclusion Criteria
 - Did not have a live birth (for those who are post-birth)
 - Self-reported major medical/health issue which would impact participants' health or ability to participate.

4 STUDY OBJECTIVES

4.1 Primary Objective

The primary objective of these analyses is to evaluate the performance of the pilot instruments selected as measures of the five outcome domains (social support, resilience, depression, anxiety, and COVID-19 mental health impacts) in the target population. Pilot instruments chosen for each of the outcome domains are as follows:

- MOS Social Support Survey
- Connor-Davidson Resilience Scale
- Edinburgh Postnatal Depression Scale
- State-Trait Anxiety Inventory (Form Y-2 - Trait Questionnaire Only)
- COVID-19 and Mental Health Impacts

4.2 Secondary Objectives

There are two secondary objectives for these analyses: 1) to summarize the feedback provided on the content and approach of the Joyuu tool, and 2) to evaluate the impact of the product through change in the pilot outcome measures after 1-month of accessing the web tool.

While change in outcomes is not a foremost objective, it is an important element of the feasibility assessment to determine whether this product shows potential in preparation for Phase II at which point we will conduct a full-scale randomized trial to measure effectiveness.

5 ANALYSIS ENDPOINTS

5.1 Primary Endpoint

The primary endpoint of these analyses is the distribution of responses for the pilot instruments selected as outcome measures at baseline and after 1-month of using the web tool.

5.2 Secondary Endpoints

The secondary endpoints for these analyses include:

1. Descriptive summarization of demographic, descriptive, and pilot feedback pre- and post-test questions.
2. Change from baseline to 1-month in summary scores for the pilot instruments included as part of the primary outcome.

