6.2 Outcome Measures

MOS Social Support Survey (19 items)

(<https://cadc.ucsf.edu/sites/g/files/tkssra881/f/Description%20and%20Scoring%20Instructions%20MOS%20Social%20Support%20Survey.pdf>)

Summary Score for Overall Social Support and 4 Subscales (Emotional/Informational Support; Tangible Support; Affectionate Support; Positive Social Interaction)

- Pre-Test Q81, Q90, Q91, Q92
- Post-Test Q81, Q90, Q91, Q92

Connor-Davidson Resilience Scale (10 items) (<https://www.sralab.org/rehabilitation-measures/connor-davidson-resilience-scale-10-item>)

Overall Summary Score

- Pre-Test Q62, Q93
- Post-Test Q62, Q93

Edinburgh Postnatal Depression Scale (10 items)

(<https://www.fresno.ucsf.edu/pediatrics/downloads/edinburghscale.pdf>)

Overall Summary Score

- Pre-Test Q64, Q65, Q66, Q67, Q68, Q69, Q70, Q71, Q72, Q73
- Post-Test Q64, Q65, Q66, Q67, Q68, Q69, Q70, Q71, Q72, Q73

State-Trait Anxiety Inventory (Form Y-2 - Trait Questionnaire Only) (20 items)

(http://oml.eular.org/sysModules/obxOml/docs/ID_150/State-Trait-Anxiety-Inventory.pdf)

- Pre-Test Q75
- Post-Test Q75

COVID-19 and Mental Health Impacts (12 items)
(<https://www.phenxtoolkit.org/protocols/view/960101>)

- Pre-Test Q79
- Post-Test Q79

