7.0 Current Status

Analysis, manuscripts and programming are currently ongoing. Additional information is pending to protect proprietary information.

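### Do two of the five instruments need a named summary score before change can be reported on them?

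*SAP*

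**What the plan says.** SAP section 4.1 sets out "the five outcome domains (social support, resilience, depression, anxiety, and COVID-19 mental health impacts" and assigns one instrument to each. Section 5.1 makes the primary endpoint the distribution of responses on those instruments, at baseline and at one month. Section 5.2 then adds, as its second secondary endpoint, "Change from baseline to 1-month in summary scores for the pilot instruments included as part of the primary outcome". The objective behind that endpoint, in section 4.2, is "to evaluate the impact of the product through change in the pilot outcome measures after 1-month of accessing the web tool". Neither statement leaves an instrument out.

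Section 6.2 lists the instruments one by one. Under social support it gives "Summary Score for Overall Social Support and 4 Subscales". Resilience and depression each carry a line naming an overall score. The entries headed "State-Trait Anxiety Inventory (Form Y-2 - Trait Questionnaire Only) (20 items" and "COVID-19 and Mental Health Impacts (12 items" carry no such line, only a link and the pre-test and post-test question numbers.

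Section 7.0 says of the rest of the plan: "Additional information is pending to protect proprietary information".

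**The concern.** An endpoint defined on summary scores needs a score for each instrument it covers. Three of the five have one in section 6.2 and two do not. The section's own layout makes the difference visible: every instrument has a link, and three also have a score line, so the link does not seem to have been meant to do the work of the score line.

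Two readings then appear possible. On the first, change is reported for all five instruments and the analyst chooses the score for two. On the second, change is reported only where section 6.2 names a score, and anxiety and COVID-19 impacts appear only as response distributions. The second would leave no change result for anxiety, although section 3 describes the tool's approaches as "including managing stress/distress, depression and anxiety related to the postpartum period". Section 7.0 also says that analysis is under way, so a score settled now could be settled with the data in view.

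**Working it through.** The documents give no figure to reproduce on this point. The check is a count, followed by a comparison of sections.

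**Count (items from section 6.2).**
- All items: 19 + 10 + 10 + 20 + 12 = 71.
- Items on the two instruments without a score line: 20 + 12 = 32, and 32/71 = 45%.
- Change scores already named: 5 for social support (overall plus 4 subscales) + 1 for resilience + 1 for depression = 7.
- With one total for each of the other two: 7 + 2 = 9. This assumes that the COVID-19 measure has a total.

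**Which reading the text supports.** Sections 4.2, 5.1 and 5.2 all refer to the pilot instruments without restriction, and section 4.1 says there are five. The three-instrument reading rests only on a missing label in a list whose main job is to map instruments to question numbers. The five-instrument reading is clearly the stronger.

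**Trait anxiety.** Section 6.2 restricts the instrument to one form, gives 20 items and places them all in one block (Q75 at both time points). It names subscales for social support and none here. Little is left to choose, and a single total is the natural summary.

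**COVID-19 impacts.** This is the part that stays open: 12/71 = 17% of the items. The public text does not say whether a total exists.
- If it does, the secondary endpoint applies to it directly.
- If it does not, there is no summary score for that endpoint to act on, and the 12 items are still reported at baseline and one month under section 5.1.

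**Could the choice produce chance findings?** Suppose item-level changes were each given a 95% interval and there were no true change. One total would exclude zero 5% of the time. At least one of 12 items would do so with probability 1 − 0.95^12 = 46% if independent, or 40%, 32% or 23% if item changes correlate 0.3, 0.5 or 0.7. The intervals, correlations and complete pairs are all assumptions; the public SAP states no test or interval. Item-level change is also not change in a summary score, so this calculation describes something outside the endpoint. On the same footing the 7 undisputed scores would give 1 − 0.95^7 = 30% if independent. The figures show what follows from many unadjusted looks. They do not measure the cost of a missing score line.

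**The case for a change.** The best argument for acting is that the remedy is cheap and the timing awkward. Resilience and depression are also single-score instruments in section 6.2, and each still received an explicit line, so an obvious total was not thought too obvious to state. A link does not say which score is the endpoint. The two entries show no sign of redaction. Section 4.2 treats change as part of judging whether the product merits Phase II, and a summary chosen during analysis is weaker than one fixed beforehand.

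Much of this stands as description: the entries are uneven, and the public text does not close the question for the COVID-19 measure. It does not show that anything would be analysed wrongly. Adding a line would record a choice without improving a method. Wording added now would itself come after recruitment, so it could not supply the advance commitment whose absence is the complaint. If the authors did intend change for only three instruments, a mandatory anxiety score would add an outcome late.

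The appeal to section 3 is also weaker than it looks. That section asks whether users find the tool's approaches to managing anxiety engaging and helpful, which is a question about feedback and does not promise a change in anxiety scores.

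**Conclusion.** The observation is accurate, but it does not call for a change. It concerns two labels in section 6.2, and in practice one instrument of 12 items. The primary endpoint is unaffected because it is a distribution of responses and needs no summary score; all 32 items are reported at both time points whichever reading is taken. The affected endpoint is secondary. Section 4.2 itself ranks change below the main aims and leaves effectiveness to a full-scale randomized trial.

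The conclusion rests on three assumptions. First, the analyst takes the plain reading of section 5.2 and covers all five instruments where a summary score exists. Second, change is described and not used as a formal test or a pass mark for Phase II; the public text states neither. Third, nothing in the linked sources or the pending material conflicts with a single total for the trait form. Those sources could not be consulted, so what can be said with confidence is that the public text omits the two lines, not that the full plan lacks them.

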6 ANALYSIS SETS, OUTCOME MEASURES, & SAMPLE SIZE DETERMINATION

6.1 Analysis Sets

The Intent-to-treat (ITT) analysis set includes all subjects who consented to participate in the study and participated in the Baseline (Pre-Test) survey.

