6.3 Sample Size Determination

For the purpose of this Phase I proof-of-concept study, a sample size of 85 participants has been deemed adequate. Actual numbers recruited differed slightly and will be reported.

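### With any loss to follow-up, the baseline and one-month distributions in SAP 5.1 describe different people; showing the returners' own baseline is a cheap improvement

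*SAP*

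**What the plan says.** Four parts of the SAP bear on this.

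- **Who is analysed.** Section 6.1 defines a single set, labelled intent-to-treat, which "includes all subjects who consented to participate in the study and participated in the Baseline (Pre-Test) survey". A post-test is not required for membership.
- **Primary endpoint.** Section 5.1 names the "distribution of responses for the pilot instruments selected as outcome measures at baseline and after 1-month of using the web tool".
- **Secondary endpoint.** Section 5.2, item 2, is "Change from baseline to 1-month in summary scores for the pilot instruments included as part of the primary outcome". It does not say whether change will be shown as a mean, a distribution or both. Section 6.2 lists the depression scale with an overall summary score and nothing further.
- **Use.** Section 4.2 ranks change below the main objective but makes it part of the feasibility assessment, "to determine whether this product shows potential in preparation for Phase II".

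Follow-up is one measurement. Of participants, section 3 says: "They will also complete a post-test after one month of having access to the tool". The visible text gives no expected retention, no rule for a participant without a post-test, and no comparison of those who return with those who do not. Section 7.0 states that further information is being held back as proprietary, and no analysis-methods section appears in the text available.

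**The concern.** A baseline distribution and a one-month distribution side by side invite the reader to compare them. Under section 6.1 the baseline column contains everyone with a pre-test. Unless everyone returns or missing values are filled in, the one-month column contains only those who completed the post-test. If people with higher depression scores at baseline return less often, the one-month column looks better with no change in any individual.

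The paired change in 5.2(2) avoids that artefact because each person is compared with herself. It has two limits of its own. It says nothing about people who did not return. And if it is shown only as a mean, improvement in some participants offsets worsening in others, so the reader cannot tell how many worsened.

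Helping with depression and anxiety is among the aims of the tool in section 3, and the one-month results inform the judgement on Phase II. A shift that reflects who stayed could be read as promise.

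**Working it through.** **The plan's own figure.** Section 6.3 says "a sample size of 85 participants has been deemed adequate", and section 3 gives a range of 80 to 90. The midpoint is (80 + 90)/2 = 85, so the two agree. The 85 cannot be reproduced further, because no standard deviation, effect size, precision target or retention rate is given.

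**Inputs.** N = 85 is from section 6.3. Everything else below is assumed, because the documents give no baseline mean, spread or loss. A higher depression score is taken as worse.

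**Step 1: the composition artefact in 5.1.** Let M be the baseline mean of all N participants, L the number who do not return, and m their baseline mean. If nobody changes, the one-month mean equals the returners' baseline mean, (N·M − L·m)/(N − L). The apparent fall is therefore L·(m − M)/(N − L). Take M = 10 and m = 14.

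- 10% loss, L = 9: (850 − 126)/76 = 9.53, an apparent fall of 0.47.
- 20% loss, L = 17: (850 − 238)/68 = 9.00, an apparent fall of 1.00.
- 30% loss, L = 26: (850 − 364)/59 = 8.24, an apparent fall of 1.76.

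The fall is proportional to m − M. If non-returners averaged 12 instead of 14, it would be half as large: 18/76 = 0.24, 34/68 = 0.50 and 52/59 = 0.88. If they averaged 10, it would be zero.

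**Step 2: a check with a different make-up.** Suppose 60 people score 6 and 25 score 15, and nobody changes. The baseline mean is (360 + 375)/85 = 8.65.

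- 90% of low and 60% of high scorers return (54 and 15): 549/69 = 7.96, an apparent change of −0.69.
- 90% and 40% return (54 and 10): 474/64 = 7.41, an apparent change of −1.24.
- 90% of both return (54 and 22 after rounding): 654/76 = 8.61, an apparent change of −0.04.

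Selective loss drives the shift; loss alone does not.

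**Step 3: the paired change in 5.2(2).** In steps 1 and 2 the within-person change among returners is exactly 0, so the artefact does not enter this endpoint. Loss distorts the paired result as a statement about all participants only if non-returners changed differently. Suppose returners change by −1.5 on average. The whole-sample mean is zero if non-returners worsened on average by 1.5 × (N − L)/L:

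- 10% loss: 1.5 × 76/9 = 12.7 points.
- 20% loss: 1.5 × 68/17 = 6.0 points.
- 30% loss: 1.5 × 59/26 = 3.4 points.

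At low loss that would take a very large difference; at 30% it is less remote.

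**Step 4: what a mean alone leaves out.** Take 68 returners and a normal change score with mean −1.5 and SD 4 or 5. The share worsening by 4 points or more is 1 − Φ((4 + 1.5)/SD): 8.5% at SD 4 and 13.6% at SD 5, or about 6 to 9 people. For any rise (cut at 0.5, for whole-number scores) the share is 1 − Φ(2/SD): 30.9% to 34.5%, or about 21 to 23 people. The assumed spread includes measurement error, so a raw count of rises is partly noise.

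**The case against.** The strongest reply is that the plan's measure of impact is already the right one. Section 4.2 evaluates impact through change in the outcome measures, and 5.2(2) is a within-person change. The false fall of 0.5 to 1.8 points does not touch it. The primary objective in section 4.1 is how the instruments perform, and for that a baseline distribution in everyone with a pre-test is appropriate. Change is expressly not the leading aim, and a randomized trial is planned for Phase II. All of this stands, and it limits the consequence. It does not remove the point, because 5.1 still shows two time points whose columns need not contain the same people.

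A reader might infer that people who worsen, or who never return, cannot be seen at all under this plan. The documents do not support that:

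- Section 5.2 does not restrict change to a mean; a distribution of change fits its present wording.
- The number without a post-test follows by subtraction, because the set in 6.1 keeps everyone with a pre-test.
- Section 6.1 is silent on how a person without a post-test enters the one-month summary. It does not prescribe a completers-only column.
- Section 7.0 says that further information is held back, so nobody can say from this text that these are the sole planned analyses.

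A reader might also infer that a safety signal is being missed. No safety objective appears in the documents. The described pilot has no control group and mixes pregnant and postpartum participants, so a rise in score could not be separated from natural course or measurement noise.

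Two possible answers to the gap do not fill it. The promise in 6.3 to report actual numbers concerns recruitment, not retention. The two surveys during the month are described as covering experience with the tool, not as outcome measurements.

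**Conclusion.** The point holds as a low-cost improvement to the visible SAP text. It is not an error that invalidates the analysis. With any selective loss, the two distributions in 5.1 are not comparable and can shift with no individual change. The size is about 0.5 to 1.8 points on the depression score at 10% to 30% loss, if non-returners start 4 points above the overall mean; it is half that for a 2-point gap and zero for none. The second make-up gives 0.7 to 1.2 points. These figures show the mechanism and do not predict this study.

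The paired change is free of the artefact but describes returners only, and a mean alone would not show how many worsened. The documents do not show that the plan hides deterioration, or that its judgement on Phase II is biased.

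**What to change.** Three additions to the SAP, all from data already collected:

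- **Section 5.1.** Keep the baseline distribution for all participants. Beside the one-month distribution, show the baseline distribution of the same returners, with the number who have both tests.
- **Returners and non-returners.** Add a table of baseline depression and anxiety scores for the two groups, with the number in each.
- **Section 5.2, item 2.** For depression and anxiety, report the distribution of individual change, including the number whose score rose. State that this is descriptive only, because without a control group a rise cannot be told apart from measurement noise or natural course.

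Section 7.0 says analysis is under way, so these should be labelled as additions. If the withheld material already contains them, a cross-reference is enough. The cost is some SAP wording and two extra descriptive tables, with no new contact with participants. The one downside is that the apparent one-month shift may look less favourable.
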